1.3 Secondary Objectives

- To evaluate the rate of CR with IVEN in participants with symptomatic, treatment naïve WM at 6, 12 and 24 cycles of therapy.
- To evaluate the best overall response to IVEN in participants with symptomatic, treatment naïve WM.
- To evaluate the rate of VGPR or better at 30 months post treatment initiation.
- To evaluate median time to response, median time to major response and median time to VGPR to IVEN in participants with symptomatic, treatment naïve WM.
- To evaluate the 24-, 36-, 48-, 60-month Progression Free Survival (PFS) of IVEN in participants with symptomatic treatment naïve WM.
- To evaluate the overall survival for participants treated with IVEN
- To evaluate the time to next treatment with IVEN
- To evaluate the effect of IVEN in the bone marrow burden of disease in participants with symptomatic treatment naïve WM.
- To evaluate the impact of CXCR4 mutations on response to IVEN in participants with symptomatic treatment naïve WM.
- To evaluate the safety profile of IVEN in participants with symptomatic treatment naïve WM.
- To evaluate the impact of IVEN in the participants' QOL.

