3. PARTICIPANT SELECTION

3.1 Eligibility Criteria

Participants must meet the following criteria on screening examination to be eligible to participate. Screening evaluations including consent, physical exam, and laboratory assessments will be done within 30 days prior to Cycle 1 Day 1. Bone marrow biopsy & aspirate, and CT C/A/P will be done within 90 days prior to Cycle 1 Day 1.

- 3.1.1 Clinicopathological diagnosis of Waldenström macroglobulinemia [28].
- 3.1.2 Known tumor expression of mutated MYD88 performed by a CLIA certified laboratory.
- 3.1.3 Symptomatic disease meeting criteria for treatment using consensus panel criteria from the Second International Workshop on Waldenström macroglobulinemia [29].
- 3.1.4 Participants with symptomatic hyperviscosity (e.g. nosebleeds, headaches, blurred vision) must undergo plasmapheresis prior to treatment initiation.
- 3.1.5 Age \geq 18 years
- 3.1.6 ECOG performance status \leq 2 (see Appendix A)
- 3.1.7 Measurable disease, defined as presence of serum immunoglobulin M (IgM) with a minimum IgM level of >2 times the upper limit of normal of each institution is required
- 3.1.8 At the time of screening, participants must have acceptable organ and marrow function as defined below:
 - Absolute neutrophil count \geq 500/uL (no growth factor permitted)
 - Platelets \geq 50,000/uL (no platelet transfusions permitted)
 - Hemoglobin \geq 7 g/dL (transfusions permitted)
 - Total bilirubin $<$ 1.5 x institutional ULN
 - AST(SGOT)/ALT(SGPT) \leq 2.5 \times institutional ULN
 - Estimated GFR \geq 30 mL/min

- 3.1.9 Females of childbearing potential (FCBP) must use one reliable form of contraception or have complete abstinence from heterosexual intercourse during the following time periods related to this study: 1) while participating in the study; and 2) for at least 90 days after discontinuation from the study. FCBP must be referred to a qualified provider of contraceptive methods if needed. FCBP must have a negative serum pregnancy test at screening.
- 3.1.10 Men must agree to use a latex condom during treatment and for up to 90 days after the last dose of ibrutinib or venetoclax during sexual contact with a FCBP
- 3.1.11 Ability to understand and the willingness to sign a written informed consent document.

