5.3 Agent Administration

5.3.1 Venetoclax

All participants will begin venetoclax at 100 mg PO once daily on Cycle 2 Day 1 (+/- 2 days) for 7 days, followed by escalation to 200 mg PO once daily (Cycle 2 Day 8) for 7 days and then 400 mg PO once daily (Cycle 2 Day 15) for 14 days. If participants require dose adjustments or delays, Cycle 3 will not commence until the participant has taken venetoclax 400 mg for 7 consecutive days. Participants will continue venetoclax for a maximum of 23 cycles, or until unacceptable toxicity or disease progression. At the completion of 24 cycles of therapy participants will discontinue all protocol therapy and enter follow-up until next therapy or death.

Dose reductions due to toxicity will be permitted on information seen in Table 6-1.

The study drug venetoclax will be administered in the DFCI, or participating site, infusion room on the first dose of each dose escalation (C2D1, C2D8, C2D15, etc.) until a dose of 400 mg PO daily is reached. Otherwise, venetoclax will be self-administered, and participants will be instructed to write in a diary daily, documenting that the drug was taken. Participants will be instructed to take the study drug at approximately the same time each day. Participants will also be instructed on how to complete the diary. If a dose is missed, it can be taken up to 6 hours after the scheduled time with a return to the normal schedule the following day. If it has been greater than 6 hours, the dose should not be taken, and the patient should take the next dose at the scheduled time the next day. The missed dose will not be made up and must be returned to the site at the next scheduled visit; this must be documented in the study diary. Furthermore, they will be instructed to call the PI or research nurse if vomiting occurs. If the pills are vomited, this should be noted on the patient diary, but a replacement dose should not be taken that day. All dosages prescribed and dispensed to the participant, and all dose changes during the study must be recorded.

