5.6 Duration of Follow Up

Participants will be followed for a maximum of 6 years from Cycle 1 Day 1, with 4 years of follow-up or until death, whichever occurs first. Participants removed from protocol therapy for unacceptable adverse event(s) will be followed at a minimum until resolution or stabilization of the adverse event. Participants will be followed for progression free survival until documented disease progression or initiation of new therapy. After this, they will be followed for survival until the conclusion of the follow-up period.

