7.8.3 Other Malignancies

All new malignant tumors including solid tumors, skin malignancies and hematologic malignancies will be reported for the duration of study treatment and during any

protocol-specified follow-up periods including post-progression follow-up for overall survival. If observed, enter data in the corresponding eCRF.

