⁵Coagulation profile. Prothrombin time (PT) will be performed at screening and repeated as clinically indicated. PT will be reported as well as the international normalized ratio (INR) and PTT.

⁶For women of childbearing potential only: Serum pregnancy test is required at screening.

⁷QOLs should be performed at C1, C4, C7, C13, C19, EOT, and every 6 months thereafter through follow-up.

⁸ QOL can be collected via telephone or email

⁹ Physical exam, and weight need to be collected at every other visit starting at Cycle 7 (i.e. C7D1, C13D1, C19D).

¹⁰ Participants will undergo assessments during follow-up until time to progression or new therapy. After PD or new therapy initiation, participants will be followed for survival status only

¹¹ Participants who have experienced disease progression or started new therapy will be followed for survival status only every 6 months (+/- 2 weeks)

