11.1.2 Response Criteria Modified VIth IWWM (NCCN 2014)

Participants may undergo plasmapheresis when clinically indicated. Those who undergo plasmapheresis will be unevaluable for any response assessment for 28 days. If plasmapheresis occurs between screening and Cycle 1 Day 1, the screening serum IgM should be used for response determination.

Complete Response (CR): A complete response (CR) is defined as having resolution of WM related symptoms, normalization of serum IgM levels with complete disappearance of IgM paraprotein by immunofixation, and resolution of any adenopathy or splenomegaly. A complete response requires reconfirmation demonstrating normal serum IgM levels, and absence of IgM paraprotein by immunofixation by a measurement repeated at least 2 weeks later.

Very Good Partial Response (VGPR): is defined as $\geq 90\%$ reduction in serum IgM levels, or normalization of serum IgM levels with persistent IgM monoclonal spike in SPEP or immunofixation.

Partial Response (PR): Partial response (PR) is defined as achieving a $\geq 50\%$ reduction in serum IgM levels.

Minor Response (MR): A minor response (MR) is defined 25-49% reduction in serum IgM levels.

Progressive Disease (PD): Progressive disease (PD) is defined as occurring when a greater than 25% increase in serum IgM level occurs with an absolute increase of at least 500 mg/dL from the lowest attained response value, or progression of clinically significant disease related symptom(s). Reconfirmation of the initial IgM increase is required when IgM is the sole criterion for progressive disease confirmation. Death from any cause or initiation of a new anti-neoplastic therapy will also be considered a progression event. For participants on active therapy who are on an ibrutinib drug hold for > 7 days, serum IgM levels will be considered unevaluable for response assessment. Patient must be on ibrutinib for >2 consecutive weeks to be considered eligible for serum IgM response assessment. An increase of 1 cm in any axis for adenopathy, or 2 cm in the craniocaudal axis of the spleen will be considered evidence of progression of extramedullary disease. Development of Bing Neel syndrome, or other extramedullary disease manifestations, as well as disease transformation will be considered as progressive events.

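### Time to next treatment is a secondary endpoint, but the plan provides no collection of the next-therapy date for participants who progress before they are re-treated

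*Combined protocol and SAP*

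**What the plan says.** Section 1.3 lists the objective "To evaluate the time to next treatment with IVEN", and Section 13.6 repeats it as a secondary endpoint. The time-to-event definitions that follow Section 11.1.2 (headed 11.1.1 a second time) cover progression-free survival (PFS), overall survival and duration of response, but not TTNT. The only censoring sentence in Section 13.6 is written for PFS.

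Three places set what is collected once a participant progresses or starts new therapy:

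- Section 5.6 follows participants for PFS until documented progression or new therapy, and continues: "After this, they will be followed for survival until the conclusion of the follow-up period".
- Study Calendar, footnote 10: "After PD or new therapy initiation, participants will be followed for survival status only".
- Study Calendar, footnote 11: "Participants who have experienced disease progression or started new therapy will be followed for survival status only every 6 months (+/- 2 weeks").

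Section 5.3.1 reads differently. Participants who complete 24 cycles "enter follow-up until next therapy or death".

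Section 11.1.2 counts new anti-neoplastic therapy as a progression event. It also allows PD on IgM alone: "Reconfirmation of the initial IgM increase is required when IgM is the sole criterion for progressive disease confirmation".

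**The concern.** PD and the start of next therapy are separate events in this protocol. PD can rest on a reconfirmed IgM rise. The protocol's own entry rule, by contrast, starts first-line treatment only for "Symptomatic disease meeting criteria for treatment using consensus panel criteria". That rule does not govern re-treatment, but it shows that in this disease a biochemical finding and a decision to treat need not coincide. TTNT is worth listing beside PFS only if it captures that difference.

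The collection rule removes it. The first of the two events moves the participant to survival follow-up, so when PD comes first nothing provides for recording the later therapy. The gap need not be long for the date to be missed.

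Timing adds weight. Section 1.1 records that all participants were told to stop treatment as of 4/1/22 and that follow-up continues for 4 years or until death. This off-treatment period is when next therapies would be expected, and start dates that nobody has asked for become harder to recover.

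**Working it through.** The documents give no TTNT figure, so there is none to reproduce. The check has two parts.

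**1. What is collected, by order of events**

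| Order of events | Next-therapy date collected? | Basis |
|---|---|---|
| New therapy, no prior PD | Yes, by implication, because it is a PFS event | 11.1.2, time-to-event definitions |
| PD, then new therapy | No provision | 5.6, footnotes 10 and 11, no calendar row |
| Neither | Censored while assessments continue | 5.6 |

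Only two analyses are possible with these data. One censors at PD. The other counts PD as the event, which is then essentially PFS, because PFS already counts new therapy.

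**2. Illustrative size**

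Inputs:

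- PD hazard λ, low value: Section 2.3 gives 92% PFS at 18 months on single-agent ibrutinib in 30 untreated patients, so λ = −ln(0.92)/18 = 0.00463 per month. Its use beyond 18 months, and for this regimen, is an assumption.
- PD hazard λ, high value: 0.010 per month (assumed).
- Therapy without prior PD: μ = 0.002 per month (assumed).
- Median lag m from PD to therapy: 6 to 24 months (assumed), so g = ln 2/m.

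All times are exponential and deaths are ignored. With a = λ + μ:

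- True freedom from next therapy: S(t) = e^(−at) + λ[e^(−at) − e^(−gt)]/(g − a)
- Estimate if censored at PD: e^(−μt)
- Estimate if PD counts as the event: e^(−at)
- Share of next therapies captured by t: (μ/a)(1 − e^(−at)) / (1 − S(t))

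Lowest case, λ = 0.010 and m = 6, so a = 0.012 and g = 0.1155:

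- S(60) = 0.4868 + 0.010 × (0.4868 − 0.0010)/0.1035 = 0.534.
- Captured by month 70 = (0.002/0.012)(1 − 0.4317)/0.5266 = 0.0947/0.5266 = 0.18.

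Highest case, λ = 0.00463 and m = 24, so a = 0.00663 and g = 0.02888:

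- S(60) = 0.6717 + 0.00463 × (0.6717 − 0.1768)/0.02225 = 0.775.
- Captured by month 70 = 0.1120/0.2681 = 0.42.

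Censored at PD, the 60-month estimate is e^(−0.12) = 0.887 in every case.

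| λ per month | Median lag (months) | True, 60 mo | Censored at PD | PD as event | Captured by 70 mo |
|---|---|---|---|---|---|
| 0.00463 | 6 | 70.0% | 88.7% | 67.2% | 32% |
| 0.00463 | 12 | 73.0% | 88.7% | 67.2% | 35% |
| 0.00463 | 24 | 77.5% | 88.7% | 67.2% | 42% |
| 0.010 | 6 | 53.4% | 88.7% | 48.7% | 18% |
| 0.010 | 12 | 58.6% | 88.7% | 48.7% | 20% |
| 0.010 | 24 | 67.0% | 88.7% | 48.7% | 24% |

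A separate Kaplan-Meier simulation used other assumptions: 30% to 70% with PD or re-treatment by 48 months, 0% to 30% of those re-treated without prior PD, and a mean gap of 3 to 12 months. Censoring at PD gave 48-month estimates of 0.70 to 1.00 against a true 0.32 to 0.77, with 0% to 33% of next therapies by 72 months captured. The direction is the same.

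**The case against.** The strongest reply is that the date is not out of reach. Contact continues every 6 months, Section 5.3.1 points to follow-up until next therapy for those who complete treatment, and the case report forms are not among the documents. A reader might infer that TTNT cannot be measured at all after PD. The documents do not support that; they show only that collection is not planned. Section 5.3.1 does not cure this, because it names no data item or schedule and conflicts with Section 5.6 and the calendar.

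Footnote 10 is attached to the response, immunoglobulin and blood-count rows, so it could be read as ending only those assessments. Footnote 11, attached to survival status, and Section 5.6 make the survival-only reading the natural one.

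Three other inferences go too far:

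- That the plan censors TTNT at PD. It states no TTNT censoring rule. The bias belongs to one of the two analyses that the planned data allow.
- That PD and re-treatment are often far apart. The documents give no PD-to-therapy interval and no share of IgM-only PD. Section 11.1.2 also counts symptoms, nodal or splenic growth, Bing-Neel syndrome and transformation as PD.
- That new malignancies are lost after PD as well. Section 7.8.3 already orders their reporting, "including post-progression follow-up for overall survival".

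TTNT is also one of many descriptive secondary endpoints in a single-arm study. The primary endpoint, PFS and overall survival are unaffected.

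**Conclusion.** The point holds as a conflict between a listed endpoint and the stated collection rule. For participants who progress first, the plan provides no next-therapy date. TTNT from the planned data is then either biased toward longer treatment-free time, provided that therapy is more likely after PD than before it, or it is essentially PFS.

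This conclusion rests on the text and does not depend on any rate. The size does: about 53% to 77% true 60-month freedom from next treatment against about 89% if censored at PD, with about 18% to 42% of next therapies captured by month 70. The 89% merely restates the assumed rate of therapy without PD. Only the low PD hazard derives from a figure in the documents, and it is extrapolated. The numbers show direction and possible scale and are not a forecast. The matter should be corrected while follow-up is running.

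**What to change.** 1. In Section 5.6 and calendar footnotes 10 and 11, replace survival status alone with survival status plus the start date and type of first subsequent WM therapy, asked at the existing 6-monthly contact. Record the date itself: a yes/no answer would leave it known only to within about 6 months, or about 7 with the 2-week windows.
2. Align the follow-up wording in Section 5.3.1 with Section 5.6 and the calendar.
3. In the time-to-event definitions, define TTNT as Cycle 1 Day 1 to first subsequent WM therapy, not censored at PD, and censored at the last contact with known treatment status. State how death is handled.
4. For participants already past PD, recover the date and type of any next therapy at the next contact.
5. For new malignancies, add at most a cross-reference to Section 7.8.3.

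The cost is an amendment and a few fields on a contact that already takes place. No visit, procedure or sample-size figure changes.

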11. MEASUREMENT OF EFFECT

For the purposes of this study, participants should be evaluated for response every 4 weeks \pm 1 week for cycles 2, 3 and 4, and thereafter every 12 weeks \pm 1 weeks for the remaining cycles, and within 4 weeks \pm 2 weeks from when a participant is removed from trial or when treatment is completed. IgMs measured intra-cycle during Cycle 1 and 2 should not be used for response or nadir determination. Post-treatment, patients will continue to be followed-up every 12 weeks \pm 2 weeks for 3 years. Participants will be assessed for efficacy by consensus panel criteria according to section 11.1.2 below adopted from the Sixth International Workshop on WM [30].

11.1 Antitumor Effect – Hematologic Tumors

11.1.1 Definitions

Evaluable for toxicity: All participants who receive at least one dose of study treatment will be evaluable for toxicity from the time of their first treatment.

Evaluable for response: Only those participants who have measurable disease present at baseline, have received at least one cycle of therapy, and have had their disease re-evaluated will be considered evaluable for response. These participants will have their response classified according to the definitions stated below. (Note: Participants who exhibit objective disease progression or die prior to the end of cycle 1 will also be considered evaluable.)

11.1.2 Response Criteria Modified VIth IWWM (NCCN 2014)

Participants may undergo plasmapheresis when clinically indicated. Those who undergo plasmapheresis will be unevaluable for any response assessment for 28 days. If plasmapheresis occurs between screening and Cycle 1 Day 1, the screening serum IgM should be used for response determination.

Complete Response (CR): A complete response (CR) is defined as having resolution of WM related symptoms, normalization of serum IgM levels with complete disappearance of IgM paraprotein by immunofixation, and resolution of any adenopathy or splenomegaly. A complete response requires reconfirmation demonstrating normal serum IgM levels, and absence of IgM paraprotein by immunofixation by a measurement repeated at least 2 weeks later.

Very Good Partial Response (VGPR): is defined as $\geq 90\%$ reduction in serum IgM levels, or normalization of serum IgM levels with persistent IgM monoclonal spike in SPEP or immunofixation.

Partial Response (PR): Partial response (PR) is defined as achieving a $\geq 50\%$ reduction in serum IgM levels.

Minor Response (MR): A minor response (MR) is defined 25-49% reduction in serum IgM levels.

Progressive Disease (PD): Progressive disease (PD) is defined as occurring when a greater than 25% increase in serum IgM level occurs with an absolute increase of at least 500 mg/dL from the lowest attained response value, or progression of clinically significant disease related symptom(s). Reconfirmation of the initial IgM increase is required when IgM is the sole criterion for progressive disease confirmation. Death from any cause or initiation of a new anti-neoplastic therapy will also be considered a progression event. For participants on active therapy who are on an ibrutinib drug hold for > 7 days, serum IgM levels will be considered unevaluable for response assessment. Patient must be on ibrutinib for >2 consecutive weeks to be considered eligible for serum IgM response assessment. An increase of 1 cm in any axis for adenopathy, or 2 cm in the craniocaudal axis of the spleen will be considered evidence of progression of extramedullary disease. Development of Bing Neel syndrome, or other extramedullary disease manifestations, as well as disease transformation will be considered as progressive events.

Stable Disease (SD): Stable disease is defined as having <25% change in serum IgM levels, in the absence of new or increasing adenopathy or splenomegaly and/or other progressive signs or symptoms of WM.

Overall Response Rate (ORR): Includes patients who achieved MR, PR, VGPR and CR.

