13. STATISTICAL CONSIDERATIONS

This is a single-arm open-label Phase II study to evaluate the safety and efficacy of Ibrutinib combined with Venetoclax (IVEN) in symptomatic, treatment naïve WM patients.

Study treatment for all participants was terminated by the Sponsor-Investigator in March of 2022 due to 4 events of ventricular arrhythmia. As of 4/1/22 all participants were notified and instructed to stop study treatment and accrual was permanently discontinued.

13.1 **Study Design/Endpoints**

The primary endpoint of the current study is:

- To evaluate the rate of VGPR or better of the combination Ibrutinib + Venetoclax (IVEN) in participants with symptomatic, treatment naïve WM, within 24 months of therapy.

13.2 **Sample Size, Accrual Rate and Study Duration**

Following a Fleming’s one step approach, and assuming a null (H0) VGPR or better rate of 25% (based on previous experience on single-agent ibrutinib efficacy in previously untreated patients with WM), and an alternative (H1) VGPR rate of 45%, a total of 50 evaluable patients need to be accrued to show the proposed difference with an alpha (2-sided type I error) of 0.03 and a power (1-beta or type II error) of 87%. Assuming 10% drop out or unevaluable rate, up to 55 participants will be enrolled. If 19 or more participants obtain a VGPR then the combination of ibrutinib and venetoclax warrants further evaluation. If fewer than 19 participants obtain a VGPR, the combination should not continue further evaluation.

Accrual Targets					
Ethnic Category	Sex/Gender				
	Females		Males		Total
Hispanic or Latino	2	+	6	=	8
Not Hispanic or Latino	10	+	32	=	42
Ethnic Category: Total of all participants	12 (A1)	+	38 (B1)	=	50 (C1)
Racial Category					
American Indian or Alaskan Native		+		=	
Asian		+	1	=	1
Black or African American	1	+	1	=	2
Native Hawaiian or other Pacific Islander		+		=	
White	11	+	36	=	42
Racial Category: Total of all participants	12 (A2)	+	38 (B2)	=	50(C2)
	(A1 = A2)		(B1 = B2)		(C1 = C2)

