13.6 Analysis of Secondary Endpoints

The secondary endpoints are:

- To evaluate the rates of CR with IVEN in participants with symptomatic treatment naïve WM at 6, 12 and 24 cycles of therapy.
- To evaluate the best overall response to IVEN in participants with symptomatic, treatment naïve WM.
- To evaluate the rate of VGPR at 30 months post treatment initiation. To evaluate median time to response, median time to major response and median time to VGPR to IVEN in participants with symptomatic, treatment naïve WM.
- To evaluate the 24-, 36-, 48-, 60-month Progression Free Survival (PFS) of IVEN in participants with symptomatic treatment naïve WM.
- To evaluate the overall survival of participants treated with IVEN
- To evaluate the time to next treatment with IVEN
- To evaluate the effect of IVEN in the bone marrow burden of disease in participants with symptomatic treatment naïve WM.
- To evaluate the impact of CXCR4 mutations on response to IVEN in participants with symptomatic treatment naïve WM.
- To evaluate the safety profile of IVEN in participants with symptomatic treatment naïve WM.
- To evaluate the impact of IVEN in the participants' QOL.

Continuous variables will be presented as medians and interquartile ranges. Categorical variables will be presented as numbers and proportions. Responses will be defined based on the criteria established by the 6th International Workshop on WM. Secondary outcomes will include the rate of VGPR at 30 months from treatment initiation, and the rate of progression-free survival (PFS) at 24, 36, 48 and 60 months from initiation of study treatment. Overall survival will also be evaluated as a secondary endpoint.

PFS analysis will be performed using the Kaplan-Meier methodology, and participants will be censored at the time of last relevant assessment if they have not demonstrated the event of interest by the end of the study. Interim analyses for safety and efficacy will be performed when 15 patients had completed 6 and 12 months of study treatment.

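### The second VGPR limb requires a persisting IgM spike, so a participant with normal IgM, negative immunofixation, a fall under 90% and an unmet CR item is scored PR, below one whose paraprotein persists

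*Combined protocol and SAP*

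**What the plan says.** Section 11.1.2 sets the response categories, and section 13.7.2 assigns each participant in the primary analysis a category from it.

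- **CR** requires "resolution of WM related symptoms, normalization of serum IgM levels with complete disappearance of IgM paraprotein by immunofixation, and resolution of any adenopathy or splenomegaly". It must also be reconfirmed by normal IgM and "absence of IgM paraprotein by immunofixation by a measurement repeated at least 2 weeks later".
- **VGPR** is met by either of two limbs. Limb 1 is a fall in serum IgM of at least 90%, with no condition on immunofixation. Limb 2 is "normalization of serum IgM levels with persistent IgM monoclonal spike in SPEP or immunofixation".
- **PR** is a fall of at least 50%, with no upper bound and no other condition.

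Entry (3.1.7) requires "a minimum IgM level of >2 times the upper limit of normal". The primary endpoint (1.2, 13.1, 13.5) is the rate of VGPR or better. Section 13.2 tests 25% against 45% in 50 evaluable participants, and the regimen passes at 19 or more.

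**The concern.** Response categories should be ordered, so that a deeper response never scores lower. Here the loss of the spike, which is a step towards CR, removes the participant from VGPR limb 2 without admitting them to CR if any other CR item is open. No text assigns that combination to a category, and the PR definition catches it.

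The boundary crossed is the one the primary endpoint uses. The misclassification therefore runs only one way, against the regimen. It falls on the kind of participant section 2.4 hopes to see, since that section justifies the combination by the need for deeper responses than ibrutinib alone gives. If scorers instead override the text case by case, primary-endpoint categories in an open-label trial rest on unrecorded judgement.

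**Working it through.** **1. The plan's own figure.** Inputs from 13.2: n = 50, pass at 19 or more, p0 = 0.25, p1 = 0.45. With X binomial(50, p), P(X ≥ 19 | 0.25) = 0.0287 and P(X ≥ 19 | 0.45) = 0.8727. These match the stated 0.03 and 87%. (The 0.0287 is a one-sided tail although 13.2 labels alpha as two-sided; that is a separate matter.)

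**2. The definitions applied to a matched pair.** Let B be baseline IgM and f the IgM reached, both in multiples of the upper limit of normal (ULN). The fall is 1 − f/B. Take B = 4 and f = 1, so the fall is 1 − 1/4 = 75%, with one residual node and no progression.

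| | Spike persists | No spike, immunofixation negative |
|---|---|---|
| CR | No | No (residual node) |
| VGPR limb 1 (fall ≥90%) | No | No |
| VGPR limb 2 (normal IgM with spike) | Yes | No |
| Category | VGPR | PR |

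**3. Where the inversion occurs.** Limb 1 fails when 1 − f/B < 0.90, that is, when B < 10f. Normal IgM means f ≤ 1, and entry means B > 2 (taking baseline as the eligibility value). Any normalisation is then a fall above 50%, and PR is the floor.

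- With IgM exactly at ULN (f = 1), the fall is 66.7% at B = 3, 80% at B = 5, 87.5% at B = 8 and 90% at B = 10. The inversion exists for B below 10.
- With IgM lower in the normal range, the band shrinks. B = 5 with f = 0.5 is a fall of 90%, and B = 8 with f = 0.75 is 90.6%. Both are VGPR by limb 1 whatever the immunofixation.

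**4. What the documents say about baseline IgM.** The only figure is in 2.5: a median of 3610 mg/dL in the earlier ibrutinib study of relapsed or refractory disease. ULN is not given. If it is assumed to lie between 200 and 400 mg/dL, normalising from 3610 is a fall of 94.5% (1 − 200/3610) to 88.9% (1 − 400/3610). It is at least 90% for any ULN up to 361. A participant at that median would therefore mostly be outside the band.

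**5. Sensitivity of the design.** The share q of participants in the gap is not in the documents. Assume that the 45% alternative describes responders under a rule without the gap, and that the current wording moves q of all participants to PR. Then P(X ≥ 19 | 0.45 − q) is:

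| q | Expected number of 50 | Power |
|---|---|---|
| 0 | 0 | 87.3% |
| 1% | 0.5 | 84.1% |
| 2% | 1 | 80.4% |
| 4% | 2 | 71.5% |
| 6% | 3 | 61.0% |

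If the 45% was set under the current wording, the design loses no power. The table shows sensitivity and is not an estimate.

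**The case against.** **Few participants can be in the gap.** They need normal IgM, no spike, a fall under 90%, an unmet CR item and no progression, all at once. This stands. It limits the size but does not restore the ordering.

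**The gap is often transient.** Under the within-24-cycles reading in 1.2, a participant already seen with normal IgM and a persisting spike has reached VGPR before the spike disappears. Regular response visits and the calendar's provision for CT and marrow to confirm CR will settle many reconfirmations. This stands in part. A residual node or symptom is not cured by a repeat sample, and the at-24-months wording in 13.5 would not credit an earlier visit.

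**The criteria come from a consensus workshop, and the 25% null from earlier ibrutinib experience.** Whether the gap is in the source, and how the earlier responses were scored, cannot be checked from the documents. The section heading calls the criteria modified, so the trial owns the text. The comparability worry is fair and argues for reporting both rates.

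**Treatment and accrual have stopped.** The rule of 19 in 50 may never be applied as designed, and the documents do not give the number enrolled. This stands, so no effect on the go decision can be claimed. The rate will still be reported, and each participant weighs more if there are fewer than 50.

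**Stronger readings the documents do not support.** A reader might infer that every participant with negative immunofixation who misses a CR item is scored PR; limb 1 rules that out for falls of 90% or more. A reader might infer that all baselines from 2 to 10 times ULN are exposed; that holds only when IgM settles at ULN. A reader might also take "If 19 or more participants obtain a VGPR" in 13.2 and "the rate of VGPR at 30 months from treatment initiation" in 13.6 to leave out confirmed CRs. Sections 1.2, 1.3, 13.1 and 13.5 and the null hypothesis in 13.2 all include better responses, so this is shorthand.

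**Conclusion.** The point holds in a narrow form. Read literally, 11.1.2 ranks a participant without progression who has normal IgM, no spike, a fall under 90% and an unmet CR item below an otherwise identical participant whose paraprotein persists. The result crosses the primary-endpoint boundary and can only reduce the VGPR-or-better count.

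The affected band is baseline IgM below 10 times the level reached. The number of participants in it is not derivable and is probably small. A claim that a material share is exposed has no support: one median from a different, previously treated population gives no distribution, and under most plausible ULN values it lies outside the band. The power figures rest entirely on assumed values of q. This is worth correcting because it is a logical fault in the primary endpoint and can be repaired with data already collected.

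**What to change.** In 11.1.2, keep limb 1 and reword limb 2 as normalisation of serum IgM, without progression, that does not meet all CR criteria, whether or not a monoclonal IgM is detectable. State that a CR awaiting or lacking reconfirmation is scored VGPR.

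List each participant whose category changes, with baseline IgM, IgM reached, immunofixation result and the CR item not met. Report the VGPR-or-better rate under both the current and the corrected wording. As an editorial change only, write VGPR or better in the 13.2 decision rule and the 13.6 30-month endpoint.

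The cost is a short amendment and a re-scoring of existing IgM, immunofixation and clinical records, with no new assessments. The drawback is a late change to an endpoint category in an open-label trial, and one that can only move participants upward. Reporting both rates lets the reader see exactly what it changed.
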